#### **8.2.7.3. Adverse Events That Cause Discontinuation**

Adverse events leading to discontinuation of treatment will be recorded and narratives will be generated for AEs that caused discontinuation.

#### **8.2.7.4. Disease Worsening**

Any medically significant worsening in DM or a flare, as judged by the investigator, will be recorded as an AE.

#### **8.2.7.5. Procedures for Assessing and Recording Adverse Events and Serious Adverse Events**

Throughout the duration of the study, the investigator or designees will closely monitor each subject. All AEs which occur during the study will be recorded, whether observed by the investigator or by the subject and whether thought to be related or unrelated to study product. The description of the AEs as recorded on the eCRF will include a description of event, start date, stop date, intensity, if it was serious, relationship to study product, what actions were taken with respect to the study product, if treatment was required and the subject's outcome.

The investigator must evaluate each AE for its relationship to the study product and for its seriousness. All AEs related to study product must be followed until resolution or until they become stable.

#### **8.2.7.6. Time Period and Frequency for Event Assessment and Follow-Up**

Safety events will be assessed from the time of signing of IC through the last visit which can include a withdrawal visit. At each study visit, the investigator will inquire about the occurrence of AEs since the last visit. All AEs considered related to study product must be followed until resolution or until they become stable.

#### **8.2.7.7. Classification of an Adverse Event**

##### **Severity of Event**

Severity is used to describe the intensity of a specific AE. The following standard with 3 grades will be used to measure the severity of AEs, including abnormal clinical laboratory values and SAEs:

- Mild: No disruption of normal daily activities.
- Moderate: Affect normal daily activities.
- Severe: Inability to perform daily activities.

##### **Relationship to Study Intervention**

After naming and grading the AE, the investigator must assign an attribution to the AE using the following categories:

Relationship	Attribution	Description
Unrelated to study product	Unrelated	The AE is clearly not related to the study product
	Unlikely	The AE is doubtfully related to the study product. Disease or other concomitant medications provide more plausible explanations for the AE. Time to drug intake makes a relationship with AE improbable
Related to study product	Possible	The AE may be related to the study product. AE could also be explained by disease or other drugs. Reasonable time relationship to drug intake
	Probable	The AE is likely related to the study product. AE is unlikely to be attributed to disease or other drugs. AE has a plausible time relationship to drug intake
	Definite	The AE is clearly related to the study product. AE cannot be explained by disease or other drugs. AE has a plausible time relationship to drug intake

Adverse events listed as ‘possibly, probably, or definitely’ related to the study product are considered to have a suspected ‘reasonable causal relationship’ to the study product.

#### **8.2.7.8. Reporting Procedures**

The reporting of the study will comply with all relevant regulatory authorities and site-specific EC requirements.

### **Controlled Substance Reporting**

As required, the site pharmacist or investigator or designee will complete and keep a copy of controlled substance forms.

### **Unanticipated Problem Reporting to Competent Authorities and Ethics Committees**

Unanticipated problems are events that may occur during a clinical trial which do not fall within the definition of suspected unexpected serious adverse reaction (SUSAR) and thus are not subject to the reporting requirements for SUSARs, even though they may be relevant in terms of subject safety. Examples include:

- An SAE which could be associated with the trial procedures and which could modify the conduct of the trial;
- A major safety finding from a newly completed animal study (such as carcinogenicity).

In relevant countries, incidents or events that meet the criteria for unanticipated problems, may need to be reported to the EC or competent authority. This information is to be reported to the Sponsor using the AE eCRF within 24 hours of learning of the event.

### **SAE Reporting**

All SAEs must be reported immediately to the Sponsor (or their designated representative) no more than 24 hours after becoming aware of the event.

Any AE that meets the specified SAE criteria ([Section 8.2.7.2](#)) will be recorded on an SAE eCRF, by the investigator or qualified designee. The investigator must complete the SAE eCRF immediately, which will prompt an electronic notification to the Sponsor or designated representative. Follow-up information on the SAE will be provided in a timely manner to the Medical Monitor and recorded on eCRF form(s). If eCRF is unavailable, paper forms must be completed and submitted to the Sponsor or designated representative expediently to maintain the reporting timelines.

The mandatory reporting of safety events to regulatory authorities will be followed as required by applicable regulatory authority, and as per the applicable reporting timelines. Reporting to Corbus, regulatory agencies, ECs, and investigators will be in accordance with all applicable local laws and regulations.

### **Reporting Events to Subjects**

Any change in benefit-risk assessment relating to lenabasum administration will be reported to study subjects in compliance with applicable local laws and regulations.

### **Reporting of Pregnancy**

Pregnancy itself is not an AE. The effect of lenabasum in pregnancy is unknown. Women subjects of childbearing potential will be instructed to inform the investigator if they become pregnant during the study or within 4 weeks after taking the final dose of study product. If the pregnancy occurs during the treatment period, the investigator should immediately discontinue the study product and instruct the subject to return any unused portion of study product to the study staff. Pregnancies occurring while the subject is on lenabasum or within 4 weeks after the subject's last dose of lenabasum should be reported by the site to the Sponsor within 24 hours of

the site being made aware. The investigator will counsel the subject about the risks of the pregnancy and the possible effects on the fetus.

To report pregnancies in subjects, the investigator or qualified designee must submit a Pregnancy Reporting Form to the Sponsor (or their designated representative) within 24 hours after learning of the pregnancy. The pregnancy must be reported to the EC within 24 hours of the investigator's knowledge of the pregnancy. The subject should be referred to an obstetrician/gynecologist experienced in reproductive toxicity for further evaluation and counselling. The investigator or qualified designee will follow the subject until completion of the pregnancy or 30 days after the birth, as applicable, and report follow-up findings to the EC.

Please note that pregnancy in the female partner of a male study subject is also a reportable event, and the same timelines and reporting procedures should be followed.

If the outcome of the pregnancy meets the criteria for immediate classification as an SAE (i.e., spontaneous abortion [any congenital anomaly detected in an aborted fetus is to be documented], stillbirth, neonatal death, or congenital anomaly), the investigator should follow the procedures for expedited reporting of SAEs to the EC within 24 hours of knowledge of the event. All neonatal deaths that occur within 30 days of birth should be reported as SAEs without regard to causality.

## 9. STATISTICAL CONSIDERATIONS

### 9.1. Statistical Hypotheses

#### 9.1.1. Primary Efficacy Endpoint

Week 28 TIS:

$H_0$ : The difference in the TIS between the active group and placebo (lenabasum group – placebo) at Week 28 = 0.

$H_1$ : The difference in the TIS between the active group and placebo (lenabasum group – placebo) at Week 28  $\neq 0$ , with superiority of active to placebo claimed if the difference between the active group and the placebo group  $> 0$  (i.e., indicates greater improvement in the active group).

### 9.2. Sample Size Determination

This study is expected to Screen 200 subjects with 150 subjects anticipated to be dosed at a ratio of 2:1:2; 60 subjects in the lenabasum 20 mg BID cohort, 30 subjects in the 5 mg BID cohort, and 60 subjects in the placebo cohort. Given 150 dosed subjects, it is expected that 120 subjects will complete at least Week 28 assuming a ~20% drop out rate. This is based on a TIS treatment group difference of 15.0, standard deviation (SD) 20.00, Alpha 0.05 two-sided, Power 95%.

The final number of subjects to be dosed will be decided based on a blinded interim analysis to assess variability in the TIS score as described in the SAP and [Section 9.4.7](#).

### 9.3. Populations for Analyses

There are 4 analysis populations defined in this study:

**The modified intent to treat (mITT) population** will consist of all randomized subjects who have received at least one dose of study product. Analysis of the modified ITT population will be used as the primary efficacy analyses and will analyze subjects under the treatment to which they were randomized, regardless of compliance with assigned treatment.

**The per protocol (PP) population** will consist of subjects who complete the study without major protocol violations deemed likely to affect the efficacy outcomes of interest (these deviations will be classified during a blinded deviation review meeting before unblinding the study). Analysis on the PP population will be used as secondary efficacy analyses, analyzing subjects under the treatment actually received.

**The safety population (SAF)** will consist of all subjects who received any study product. Analysis performed on the safety population will be according to the treatment actually received.

**The pharmacokinetic (PK) population** will consist of all subjects from the SAF whose pharmacokinetic data are adequate for the calculation of primary PK parameters. Inclusion in the PK population of subjects with missing data or protocol violations or inadequate dosing will be considered on a case-by-case basis. The PK population will be the analysis set used for all pharmacokinetic analyses.

## **9.4. Statistical Analyses**

### **9.4.1. General Approach**

All data will be provided in data listings sorted by treatment group, subject number, and visit. Summary data will be presented in tabular format by treatment group. Categorical data will be summarized by the number and percentage of subjects in each category. Continuous data will be summarized by descriptive statistics including the sample size (n), mean, standard deviation, median, minimum and maximum. All percentages will be rounded to one decimal place. Differences between treatment groups will be calculated as lenabasum placebo and change from Baseline will be calculated as visit Baseline. The Baseline measure will be defined as the last non-missing measure before initiation of study product.

Data will be presented by randomized treatment group for efficacy data and by actual treatment group for safety data.

P-values and 2-sided 95% confidence intervals will be presented for all efficacy endpoints.

#### **9.4.1.1. Handling of Missing Data**

The analysis of the primary endpoint will be performed on the mITT population, using a mixed-effect model for repeated measures (MMRM), on observed data, using last observation carried forward (LOCF) for  $\leq 2$  missing core set items. If more than 2 core items are missing, the TIS score will not be calculated for that visit. Sensitivity analyses for the primary endpoint will include imputing missing data using last observation carried forward, the completer population, and the per-protocol population.

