#### 7.2.1.4. Visit 2 (Week 4 ± 1)

- Every effort should be made to remind the subject of dosing requirements for PK sampling ([Section 5.1](#)) 1-3 days prior to the scheduled visit
- Patient-reported efficacy assessments
  - PtGA
  - HAQ-DI
  - SF-36
  - PROMIS-29 Short Form
  - Patient VAS score for pain
  - FACIT-Fatigue Score
  - 5-D Itch Questionnaire
  - Skindex-29+3
  - EQ-5D questionnaire
- Collect and count capsules of returned study product
- Record concomitant medication(s)
- AE monitoring
- Contraceptive assessment and record of LMP for WOCBP
- Vital signs (including BP, pulse rate, respiratory rate, and temperature) and weight
- 12 lead ECG
- Brief physical examination
- Physician assessments of efficacy
  - MMT-8
  - CDASI score
  - IGA scale of skin activity
  - EMGA (10-cm VAS)
  - MDGA (10-cm VAS and Likert Scale)
- Laboratory tests
  - CBC with differential cell count and platelets
  - Metabolic panel (includes ALT, AST and LDH)
  - CK and aldolase
  - Urine  $\beta$ hCG in WOCBP

- Urine dipstick
- Lenabasum plasma concentration and metabolite profiling
- Dispense study product

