**7.2.1.6. Visit 4 (Week 16 ± 1)**

- Every effort should be made to remind the subject of dosing requirements for PK sampling ([Section 5.1](#)) 1-3 days prior to the scheduled visit
- Patient-reported efficacy assessments
  - PtGA
  - HAQ-DI
  - SF-36
  - PROMIS-29 Short Form
  - Patient VAS score for pain
  - FACIT-Fatigue Score
  - 5-D Itch Questionnaire
  - Skindex-29+3
  - EQ-5D questionnaire
- Patient Improvement Questionnaire for Subjects (see [Appendix 4](#))

---

 Study personnel will be required to contact subjects 3±1 weeks after Visit 9 to assess compliance and safety.

- Collect and count capsules of returned study product
- Record concomitant medication(s)
- AE monitoring
- Contraceptive assessment and record of LMP for WOCBP
- Vital signs (including BP, pulse rate, respiratory rate, and temperature) and weight
- Spirometry
- Brief physical examination
- Physician assessments of efficacy
  - MMT-8
  - CDASI score
  - IGA scale of skin activity
  - EMGA (10-cm VAS)
  - MDGA (10-cm VAS and Likert Scale)
- Patient Improvement Questionnaire for Physicians (see [Appendix 3](#))
- Laboratory tests
  - CBC with differential cell count and platelets
  - Metabolic panel (includes ALT, AST, and LDH)
  - CK and aldolase
  - Urine  $\beta$ hCG in WOCBP
- Skin biopsies (optional at selected sites)
- Lenabasum plasma concentration and metabolite profiling
- Dispense study product

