#### 7.2.1.7. Visit 6 (Week 28 $\pm$ 1)

- Every effort should be made to remind the subject of dosing requirements for PK sampling ([Section 5.1](#)) 1-3 days prior to the scheduled visit
- Patient-reported efficacy assessments
  - PtGA
  - HAQ-DI
  - SF-36
  - PROMIS-29 Short Form
  - Patient VAS score for pain

- FACIT-Fatigue Score
- 5-D Itch Questionnaire
- Skindex-29+3
- EQ-5D questionnaire
- Patient Improvement Questionnaire for Subjects (see [Appendix 4](#))
- Collect and count capsules of returned study product
- Record concomitant medication(s)
- AE monitoring
- Contraceptive assessment and record of LMP for WOCBP
- Vital signs (including BP, pulse rate, respiratory rate, and temperature) and weight
- 12 lead ECG
- Spirometry
- Brief physical examination
- Physician assessments of efficacy
  - MMT-8
  - CDASI score
  - IGA scale of skin activity
  - EMGA (10-cm VAS)
  - MDGA (10-cm VAS and Likert Scale)
- Patient Improvement Questionnaire for Physicians (see [Appendix 3](#))
- Laboratory tests
  - CBC with differential cell count and platelets
  - Metabolic panel (includes ALT, AST, and LDH)
  - CK and aldolase
  - Blood biomarkers
  - Blood for flow cytometry (optional at selected sites)
  - Urine dipstick
  - Urine  $\beta$ hCG in WOCBP
- Lenabasum plasma concentration and metabolite profiling
- Dispense study product

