#### 8.1.2. Total Improvement Score (TIS)

Efficacy will be assessed using the 2016 ACR/EULAR Myositis Response Criteria Total Improvement Score, comparing the change from Baseline between lenabasum and placebo groups.

Myositis response criteria were developed for both juvenile and adult populations and are based on a 0 – 100 scale. Six core measures are used to calculate the TIS ([Aggarwal et al., 2017](#)). Higher scores indicate better improvement in myositis.

The six measures that comprise the TIS are summarized below:

- **Physician Global Activity (MDGA):** An assessment of overall global disease activity by the physician will be done using a 10-cm VAS. The Physician Assessments should ideally be done by the same investigator. The physician should refer to subject's MDGA score from the previous visit to ensure consistency in rating.
- **Patient Global Activity (PtGA):** An assessment of overall global disease activity by the patient will be done using a 10-cm VAS.
- **Manual Muscle Testing-8 (MMT-8):** For MMT assessment, a MMT that assesses strength in 8 muscle groups (MMT-8) will be used. Strength in 8 muscle groups will be assessed on a 0 – 10 point scale (see [Table 5](#)) and recorded. Strength in the following 7

muscle groups will be assessed bilaterally: deltoid, biceps, wrist extensors, gluteus maximus, gluteus medius, quadriceps, ankle dorsiflexors. In addition, strength in the neck flexors will be assessed.

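### The primary Week 28 TIS is called observed data, yet up to two of its six core measures may be carried forward, and no named sensitivity analysis takes the carried items out

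*Protocol*

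**What the plan says.** Protocol section 9.4.1.1 sets the rule for the primary analysis. The model for repeated measures (MMRM) is run "on observed data, using last observation carried forward (LOCF) for" two or fewer missing core set items. The only condition under which no score is produced is this: "If more than 2 core items are missing, the TIS score will not be calculated for that visit".

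Section 8.1.2 gives the denominator: "Six core measures are used to calculate the TIS". The rule can therefore fill 2/6, one third, of the components.

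The named sensitivity analyses for the primary endpoint are "imputing missing data using last observation carried forward, the completer population, and the per-protocol population".

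Section 9.4.1 defines Baseline: "The Baseline measure will be defined as the last non-missing measure before initiation of study product". Neither section says how old a carried value may be, or whether Baseline may be carried.

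In Table 3 and section 7.2.1, all six core measures are collected together only at Visits 1, 2, 4, 6, 8 and 10 (Day 1 and Weeks 4, 16, 28, 40 and 52). The odd-numbered visits from Visit 3 on (Weeks 10, 22, 34 and 46) contribute only ALT, AST and LDH, as part of the metabolic panel.

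**The concern.** An MMRM on observed data is normally chosen so that missing outcomes are handled by the model under missing at random, without single imputation. Here the imputation happens one level lower, inside the score. Once a TIS has been completed with carried items it looks like any other score. The model cannot see the gap, and the standard error takes no account of it.

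Carry-forward moves the affected score towards the subject's earlier state. A subject still improving between Week 16 and Week 28 is under-credited; one who has worsened is over-credited. If partial missingness is equally common in both arms and the active arm improves more, the difference shrinks slightly. If it differs by arm, the bias does not cancel and may favour either arm.

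A reader would look to the sensitivity analyses for reassurance, but none is described as rescoring TIS without carried items. The LOCF analysis adds carry-forward. The completer and per-protocol analyses restrict the subjects and leave the scoring rule in place.

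**Working it through.** **Design figure first.** Inputs from the Synopsis and section 9.2: difference 15, SD 20, two-sided alpha 0.05, 48 completers per arm, 95% power. The normal approximation gives n = 2 × (1.960 + 1.645)² × 20² / 15² = 46.2, so 47 per arm against the stated 48. Power at 48 per arm is 95.7% (95.3% with the noncentral t). The plan's figure reproduces, and nothing below changes it.

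**Age of a value carried to Week 28**, from the visit schedule:

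| Source | Age (weeks) | Available for |
|---|---|---|
| Week 22 | 28 − 22 = 6 | ALT, AST, LDH only |
| Week 16 | 28 − 16 = 12 | all six measures |
| Week 4 | 28 − 4 = 24 | all six, if Week 16 is also missing |
| Baseline | 28 | all six, if Weeks 4 and 16 are also missing, and only because the text does not forbid it |

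The Week 22 source helps only when the enzyme used for scoring (the most abnormal at Baseline, section 8.1.2) is ALT, AST or LDH. CK and aldolase are not drawn at that visit.

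**Effect on the difference.** The protocol gives no rate of partial missingness, no arm means, and no visible item weights (the content of Appendix 6 is not shown). Assumptions: equal weights of 1/6; additive scoring; two items carried in every affected subject; Week 28 means of 35 (20 mg) and 20 (placebo), which differ by the design value of 15. The carried level is a fraction c of the Week 28 level, with c = 0.6 for Week 16 and c = 0 for Baseline.

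Arm mean after carrying = mean × [1 − f × (2/6) × (1 − c)], where f is the share of subjects affected.

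| f active / f placebo | Week 16 (c = 0.6) | Baseline (c = 0) |
|---|---|---|
| 10% / 10% | 34.53 − 19.73 = 14.8 | 33.83 − 19.33 = 14.5 |
| 15% / 5% | 34.30 − 19.87 = 14.4 | 33.25 − 19.67 = 13.6 |
| 5% / 15% | 34.77 − 19.60 = 15.2 | 34.42 − 19.00 = 15.4 |

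A harsher case, carrying from Baseline with 20% against 5%, gives 32.67 − 19.67 = 13.0. The reverse gives 34.42 − 18.67 = 15.75.

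**Power**, holding SD at 20 and n at 48 per arm, so that SE = 20 × √(2/48) = 4.08. A difference of 14.5 gives 94.4%. A difference of 13.6 gives Φ(13.58/4.08 − 1.96) = Φ(1.37), about 91%. A difference of 13.0 gives 89.0%.

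**No true difference.** If both arms average 20, Baseline carrying with 5% of active and 15% of placebo affected gives 19.67 − 19.00 = 0.67 points in favour of active. That is 0.67/4.08, or about 0.16 standard errors.

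**Do the named analyses catch it?** Per protocol (section 9.3) excludes subjects with major violations likely to affect efficacy. The listed violation about incomplete core measurements (section 10.1.10) names Visits 1 and 10, not Visit 6, where the primary endpoint is measured. The completer population is not among the four populations in section 9.3 and is not said to require all six items.

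**The case against.** The best defence is that the rule is bounded and openly stated. A visit with more than two items missing gives no TIS and is left to the model, and the phrase about observed data stands in the same sentence as the exception to it. All six measures are due at the same visits, so partial gaps may be rare. The missingness rates above are assumed, and with equal, low rates the shift is a fraction of a point against an SD of 20. The sensitivity list need not be exhaustive. The deviation list is expressly open-ended, so blinded review could remove some affected subjects from the per-protocol set. Each core measure is also reported separately. Most of this stands and keeps the point small. It does not alter the fact that the protocol itself fixes the method, or that none of these checks is stated to yield a TIS free of carried items.

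Several stronger readings are tempting but not supported:

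- **Baseline values are routinely carried.** The protocol does not say so; its silence merely permits it, and the SAP may restrict it. It would also need the same item missing at Weeks 4, 16 and 28 while at least four others are present at Week 28.
- **Week 16 is the best source for every item.** It is not for ALT, AST and LDH.
- **The TIS ≥ 40 and Week 52 tests are biased too.** The sentence concerns the analysis of the primary endpoint. Extending it to those tests is inference.
- **The rule is reliably conservative.** Unequal missingness can also enlarge the difference.

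**Conclusion.** The point holds as a modest weakness in the primary analysis. The protocol applies single imputation to as many as two of six components, analyses the result as observed, and names no analysis that removes it. The error can run in either direction.

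Its size is likely small. Under the stated assumptions a true difference of 15 is estimated as 14.5 to 14.8 with 10% affected in both arms, and as 13.6 to 15.4 with a 15% against 5% split. These figures rest on assumed missingness, arm means, equal weights and additive scoring. The top and bottom of the range require Baseline carry-forward in every affected subject. Sample size and stated power are unaffected. The point would become important only if partial missingness proved common or clearly unequal between arms.

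**What to change.** Preferred: where one or two core measures are missing at a visit, impute them under missing at random from the subject's other items and other visits, using multiple imputation so that the uncertainty is carried through. Then compute TIS and fit the MMRM. Keep item-level LOCF as a sensitivity analysis.

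Minimum: pre-specify one sensitivity analysis in which TIS is set to missing whenever any core item is missing and is left to the MMRM. Reword section 9.4.1.1 so that the LOCF-filled score is no longer described as observed data.

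Cost: wording in the protocol or SAP before unblinding, modest programming, and a slightly more complex derivation. No new data and no change in sample size are needed. The minimum analysis gives up some information. If 5%, 10% or 20% of Week 28 scores were set aside, about 45, 43 or 38 per arm would remain, with power of about 94.5%, 93.5% or 90.5% at a difference of 15 and SD 20. That count ignores what the model recovers from the other visits.

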**Study Treatment:**

All treatments: lenabasum (20 mg or 5 mg) or placebo, will be administered orally BID for up to 52 weeks.

**Study Duration:** Estimated duration for Part A is anticipated to be approximately 36 months from first subject first visit to last subject last visit and will depend on the rate of enrollment across the various sites.

**Statistical Methodology:** It is planned that about 150 subjects will be dosed at a ratio of 2:1:2 to lenabasum 20 mg, lenabasum 5 mg, or placebo arms, respectively, with a total of 120 subjects expected to complete the study (assuming  $\sim$  20% drop out rate). A total of 120 subjects (48 subjects each in the 20 mg BID and placebo groups, and 24 subjects in the 5 mg BID dose group) achieves 95% power to detect a significant difference in the TIS score between the lenabasum 20 mg BID group and placebo. This assumes a two-sided test at alpha = 0.05 and a common standard deviation of 20.00 in both treatment arms for the primary efficacy outcome, and a difference in the TIS between lenabasum 20 mg BID and placebo of 15.0. The number of subjects to be randomized may be adjusted further during the study after a blinded interim analysis of the emerging data. The intent is to perform a blinded interim examination of the variance of the TIS to potentially increase the sample size to maintain power (with no statistical adjustment to the alpha level required). The projected maximum number of subjects to be randomized is about 230 subjects (for 183 completers), which corresponds to standard deviation of 30.00, and 85% power.

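### The sensitivity analyses named for the Week 28 TIS do not vary the primary model's missing-at-random assumption, and the per-protocol set depends on completing the 52-week study

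*Protocol*

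**What the plan says.** Section 9.4.1.1 runs the primary analysis in the mITT population, "using a mixed-effect model for repeated measures (MMRM), on observed data, using last observation carried forward (LOCF) for" two or fewer missing core set items. For larger gaps: "If more than 2 core items are missing, the TIS score will not be calculated for that visit". A missing Week 28 TIS is thus left to the model, which treats it as missing at random.

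The same section lists the checks on that choice: "Sensitivity analyses for the primary endpoint will include imputing missing data using last observation carried forward, the completer population, and the per-protocol population". No other section of the protocol names an analysis that departs from MAR.

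Section 9.3 defines the per-protocol population as "subjects who complete the study without major protocol violations deemed likely to affect the efficacy outcomes of interest". Part A treatment runs to Week 52, while the primary endpoint is at Week 28. Section 9.3 defines four populations (mITT, per-protocol, safety, PK), and a completer population is not among them.

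On the amount of missing data, Section 9.2 says "it is expected that 120 subjects will complete at least Week 28 assuming a ~20% drop out rate". The Synopsis (Statistical Methodology) attaches the same 20% to completing the study.

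Three further provisions set the scope:
- **Section 4.5** asks subjects who stop study product for safety or tolerability to return at Visits 4, 6, 8 and 10, and includes their off-treatment data in the analyses. Visit 6 is Week 28.
- **Section 6.1** extends these return visits to its other listed reasons for stopping, except loss to follow-up and withdrawn consent.
- **Section 5.3.1** ends efficacy assessment for a subject who is unblinded.

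**The concern.** A sensitivity analysis for missing data should show how far the main assumption can fail before the conclusion changes. The three named analyses do something else.

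- **LOCF** replaces MAR with another fixed assumption, that nothing changes after the last visit. Before Week 28, Table 3 schedules the full core set after baseline only at Weeks 4 and 16 (or at an early termination visit), so an early score stands in for the endpoint.
- **Completers** are selected on events after randomisation.
- **Per-protocol** is selected in the same way, and on events up to Week 52. A subject with a complete Week 28 TIS who withdraws at Week 34 is excluded from a check on the Week 28 result.

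At stake is the reading of a positive primary result. Agreement with the MMRM could be taken as robustness although MAR was never varied. Disagreement could come from the bias of LOCF or of the completer set rather than from any fault in the MMRM.

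**Working it through.** **1. The plan's own figure.** Inputs: "This is based on a TIS treatment group difference of 15.0, standard deviation (SD) 20.00, Alpha 0.05 two-sided, Power 95" percent (Section 9.2); completers "48 subjects each in the 20 mg BID and placebo groups, and 24 subjects in the 5 mg BID dose group" (Synopsis); dosed "60 subjects in the lenabasum 20 mg BID cohort, 30 subjects in the 5 mg BID cohort, and 60 subjects in the placebo cohort" (Section 9.2).

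- SE = 20 × √(2/48) = 4.08.
- Power = Φ(15/4.08 − 1.96) = 95.7%, or 95.3% by the noncentral t. The stated 95% reproduces.
- 120/0.80 = 150 dosed, as stated.

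**2. Tipping shift.** The smallest significant difference is t(0.975, 94 df) × 4.08 = 8.1 points. If a share p of the active arm is missing at Week 28, and those values lie δ points below the MAR prediction, the estimate falls by p × δ. Significance is lost at δ = (D − 8.1)/p, where D is the observed difference. The documents do not give p after the return visits. The table uses the planning figure of 20% and, as an assumed alternative, 10%. The SE is held at 4.08.

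| Observed difference D | δ at p = 20% | δ at p = 10% |
|---|---|---|
| 9 | 4.5 | 9 |
| 10 | 9.5 | 19 |
| 12 | 19.5 | 39 |
| 15 | 34.5 | 69 |

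**3. Upper bound on overstatement.** Suppose 20% of each arm is missing at Week 28, nobody returns off treatment, the missing active subjects have lost all benefit, and their earlier visits gave no sign of it.

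- True difference: 0.8 × 15 + 0.2 × 0 = 12.
- MMRM and completers: both 15, and 15/12 = 1.25, a 25% overstatement.
- LOCF: 12 + 0.2 × (Week 16 effect), so between 12 and 15 for a Week 16 effect between 0 and 15.
- An imputation giving the missing active subjects placebo-like values: 12.

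With 10% missing the true difference is 0.9 × 15 = 13.5, and the overstatement is 1.5/13.5 = 11%.

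**4. Behaviour of the named analyses.** This is a simulation on assumed inputs, not figures from the protocol: placebo means 10, 18 and 25 at Weeks 4, 16 and 28; active effect 30%, 70% and 100% of its Week 28 value; SD 20; serial correlation 0.6; dropout after Week 16, with poorer responders more likely to leave. In the MAR rows dropout depends on the Week 16 score; in the not-at-random rows it depends on the unseen Week 28 score.

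| Mechanism, dropout active/placebo | True | MAR model | Completers | LOCF |
|---|---|---|---|---|
| MAR, 20%/20% | 15.11 | 15.11 | 15.10 | 14.23 |
| MAR, 30%/10% | 15.04 | 15.05 | 17.01 | 11.52 |
| MAR, 10%/30% | 14.99 | 14.98 | 13.02 | 16.68 |
| MAR, no effect, 30%/10% | −0.04 | −0.04 | 1.92 | −2.19 |
| Not at random, 20%/20% | 15.00 | 14.98 | 14.96 | 14.10 |
| Not at random, 30%/10% | 15.01 | 17.21 | 18.24 | 12.99 |

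When MAR holds and dropout is unequal, the primary model is right and both LOCF and completers are wrong, in opposite directions. When MAR fails (last row), completers err on the same side as the primary model. At 30%/10%, LOCF lies 3.5 points below the MAR model when MAR holds (15.05 − 11.52) and 4.2 below when it fails (17.21 − 12.99). A gap of that kind does not tell the reader whether the primary estimate is biased.

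**The case against.** The strongest reply is that the protocol already works to prevent the problem. Under Sections 4.5 and 6.1, subjects who stop study product are asked back at Week 28 and their data are analysed, and Section 5.5.2 prefers keeping rescued subjects in the study. Lost benefit in those who return is observed and enters the mITT model. This stands, and it limits the concern to loss to follow-up, withdrawn consent and unblinding. A reader might infer from the 20% dropout figure that a fifth of Week 28 scores will be missing and the effect overstated by a quarter. The documents do not support that: 20% is a ceiling on the planning assumption, and on the Synopsis reading, where it refers to completing the study, the Week 28 share is lower.

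A reader might also infer that the named analyses always favour the drug or could never expose a biased MMRM. That is too strong. With equal dropout, completer bias is near zero in the simulation. LOCF can err either way and can diverge visibly from the MMRM.

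Third, the list in Section 9.4.1.1 is open-ended and the SAP may add analyses that depart from MAR. That stands too, so this is not a finding that such analyses are absent from the trial. It is a finding about the three that the protocol chose to name.

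Finally, any result with p near 0.03 is fragile, and at the planned difference the shift needed is more than twice the assumed effect. This is correct and belongs in the conclusion. Section 9.3 also already gives per-protocol a secondary role, so only its completion requirement needs changing.

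**Conclusion.** The point holds in a limited form. The three named analyses do not test the assumption on which the primary result rests, and they can be biased when the primary model is not. The per-protocol definition is tied to the wrong time point for a Week 28 endpoint.

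The consequence depends on where the result falls. At an observed difference of 15 the conclusion survives any plausible departure from MAR. Between the significance threshold of 8.1 and about 10 points, a shift of 9.5 points or less in the missing active-arm values overturns it, and none of the named analyses would quantify that. These shifts assume 48 observed subjects per arm, SD 20 and 20% missing; with fewer missing the result is more robust. The 25% overstatement is an upper bound that requires 20% missing, no off-treatment Week 28 data and complete loss of benefit. It is not an expected value.

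**What to change.** In Section 9.4.1.1, name two sensitivity analyses for missing Week 28 TIS, both applied to values still missing after the off-treatment return visits:

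1. A delta-adjusted tipping-point analysis that reports the shift in missing active-arm values at which significance is lost.
2. A reference-based multiple imputation in which missing active-arm values are drawn from the placebo pattern.

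Keep LOCF and the completer analysis, if at all, as supportive only, and define the completer set. In Section 9.3, define per-protocol membership for the primary endpoint by completion of Week 28 rather than of the study.

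The cost is a change of wording in two sections, matching SAP text and a little programming. No new data are needed. The change should be made before unblinding.
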